6.2 Analysis methods

6.2.1 Primary analysis

As recommended by the CONSORT statement for non-inferiority trials, we will perform both intention-to-treat (ITT) and per-protocol (PP) analyses. For the primary outcome, ITT and PP analyses must reach the same conclusion to establish noninferiority. For secondary outcomes, the ITT analysis will be the primary analysis, the PP analysis a secondary analysis.

We will use a repeated-measures mixed-effects linear model with robust standard errogrs to compare the mean OSCE scores of both groups 6 months after the course (primary outcome) as well as immediately after the course (secondary outcome), taking into account the possible dependence of data within sites, participants, and series. The model will include the averaged OSCE score over all six stations of a series of each participant at both time points as dependent variable, fixed terms for the learning group, the type of series, the time point and the interaction term between learning group and time point, and random terms for site and participant. We will assess non-inferiority based on a one-sided 95% confidence interval for the difference in mean OSCE score between the two groups 6 months after the course. If the lower confidence limit lies above the non-inferiority margin of -1.5 points, we will claim non-inferiority. If non-inferiority can be established, we will test for superiority of the blended learning group at a two-sided alpha level of 0.05. This stepwise testing approach will keep the overall family-wise type-I error rate at the nominal 5%-level.

The difference in mean OSCE score immediately after the course will be assessed from the same model described above and presented with a two-sided 95% confidence interval and corresponding p-value.

The difference in median number of additional hours of self-training will be assessed from a quantile regression using robust standard errors to account for dependence of data within sites, and presented with a two-sided 95% confidence interval and corresponding p-value.

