6.2.3 Sensitivity analyses

As a sensitivity analysis, we will analyse the two time points separately using the same model as described above but omitting fixed terms for the time point and the interaction between time point and learning group as well as the random term for participant. In case the primary model should not fit, we will use this approach as the primary analysis.

Morover, we will analyze individual OSCE scores of each station instead of the averaged OSCE scores over all six stations within a series. We will use the same model as described above, but using a random term for station instead of a fixed term for series. We will also consider random terms for series and assessor as well as a random slope if there is non-zero variability and if the model fits. Should models not fit, we will analyse the two time points separately.

Depending on the distribution of the additional hours of self-training, we will furthermore use a non-parametric Wilcoxon-rank-sum test, a mixed-effects negative binomial model considering zero-inflation and a random term for sites, or a negative binomial model considering zero-inflation and robust standard errors for this secondary outcome.

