6.2.5 Assessment of statistical assumptions

We will assess normality and homoskedasticity of residuals of the linear model used to analyse OSCE scores based on a QQ-plot as well as a fitted-value vs. residual plot. If the distribution severely deviates from a normal distribution, we will perform adequate transformation of OSCE scores.

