6.3 Missing data

If the OSCE score of at least one station at either time point (immediately after or six months after the course) is available, repeated-measures models properly account for missing data. If more than 5% of students have completely missing

outcome data at both time points, we will perform multiple imputation in the primary analysis, and perform an available case analysis as sensitivity analysis. Chained equations will be used to impute missing data, using predictive mean matching for continuous/ordinal variables, logistic regression for binary variables, and multinomial logistic regression for categorical variables. The following variables will be considered in the imputation model: OSCE score, site, station, hours of additional training, motivation for ultrasound, age, gender, and other baseline variables listed in Table 1. The two learning groups will be imputed separately. We will generate 50 imputed data sets, which will be analysed and combined using Rubin's rule.

For the secondary outcome of additional hours of self-training, we will also use multiple imputation if the primary outcome was analysed using multiple imputation. Else, we will disregard missing data and perform an available case analysis.

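### The SAP does not secure the 6-month limit: the robust errors have no named cluster level (three sites), and the implied equal variance at both OSCEs can bias the contrast if dropout is uneven

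*SAP*

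**What the plan says.** SAP 6.2.1 states: "We will use a repeated-measures mixed-effects linear model with robust standard errogrs to compare the mean OSCE scores of both groups". The model has "fixed terms for the learning group, the type of series, the time point and the interaction term between learning group and time point", together with "random terms for site and participant". It gives no residual covariance structure, no separate variance per time point and no cluster level for the robust errors. The decision rule is: "If the lower confidence limit lies above the non-inferiority margin of -1.5 points, we will claim non-inferiority".

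Three other sections bear on this:

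- **6.2.3** adds a sensitivity analysis: "we will analyse the two time points separately using the same model as described above". It continues: "In case the primary model should not fit, we will use this approach as the primary analysis". What counts as not fitting is not defined.
- **6.2.5** plans to inspect normality and homoskedasticity of residuals, but its only remedy concerns normality: "If the distribution severely deviates from a normal distribution, we will perform adequate transformation of OSCE scores".
- **6.3** says that, once a student has a score from either time point, "repeated-measures models properly account for missing data". Multiple imputation starts only if more than 5% of students have no score at both OSCEs.

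**The concern.** With two occasions per student, a participant random intercept plus one residual variance is compound symmetry: the SD right after the course and the SD 6 months later are forced to be equal. Students may differ in how much they forget and how much they practise, so equal SDs are not assured.

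The robust errors are the plan's protection, and two questions follow.

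- Which units does the sandwich treat as independent? With a random site term the model itself makes students in one site correlated, so independence holds only between the three sites.
- Does the protection reach the estimate? A sandwich changes the standard error only. For students who miss the second OSCE, the fitted covariance decides how strongly their first score informs the 6-month mean.

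The trial's main claim is a single one-sided limit on that contrast, so both questions bear on it.

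**Working it through.** **The plan's own figure.** Inputs from SAP 3.3: SD 4, margin −1.5, assumed difference +0.5, one-sided alpha 0.05, power 90%.

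n per arm = 2 × (1.645 + 1.282)² × 4² / 2.0² = 68.5, so 69 per arm and 138 in total. Then 138 / 0.91 = 151.6, so 152. Both stated figures are reproduced. With complete data the standard error is 4 × √(2/69) = 0.681.

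**Step 1: equal variance alone.** SDs by time point are assumptions, because the SAP gives only SD 4. Under compound symmetry the fitted variance at each occasion is (SD1² + SD2²)/2, while the 6-month contrast needs SD2². With r = √[((SD1² + SD2²)/2)/SD2²], the one-sided error from *model-based* errors is 1 − Φ(1.645 r).

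| SD immediate / 6 months | r | One-sided error, model-based |
|---|---|---|
| 3.5 / 4.5 | 0.896 | 7.0% |
| 3 / 5 | 0.825 | 8.7% |
| 4.5 / 3.5 | 1.152 | 2.9% |

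The plan specifies robust errors, so these rates are not those of the planned analysis. A simulation took 152 students, a true difference of −1.5, 9% missing at 6 months regardless of arm or score, correlation 0.5, a 6-month SD of 4 and immediate SDs from 2 to 6. It ran 4,000 trials per setting, with fixed site effects standing in for the random term. With participant-level robust errors the mean standard error was 0.666 to 0.669, against an empirical 0.658 to 0.686. One-sided error was 0.044 to 0.057 throughout.

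**Step 2: clustering on site.** In the same simulation, a site-clustered sandwich with a normal quantile gave one-sided error of 0.1175 to 0.1205, including when the two SDs were equal. A closed form agrees. With three clusters the ratio behaves roughly like t on 2 degrees of freedom, for which P(T > t) = 0.5 − t / (2√(2 + t²)). At t = 1.645 this is 0.5 − 1.645/(2 × 2.169) = 0.121.

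Using the t quantile on 2 degrees of freedom instead (2.920) would restore the level. It would also widen the typical half-width from 1.645 × 0.681 = 1.12 to about 2.920 × 0.681 = 1.99, and only 2.0 points separate the assumed difference from the margin.

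**Step 3: uneven dropout.** Suppose a share p of one arm misses the second OSCE, and those students' first scores lie d below those of students who attended. The model adjusts the arm's 6-month mean by slope × p × d, so the bias is the error in the slope times p × d. Assume correlation 0.5, p = 0.09 and d equal to one immediate SD.

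| | SDs 3 / 5 | SDs 3.5 / 4.5 |
|---|---|---|
| Correct slope, ρ·SD2/SD1 | 0.833 | 0.643 |
| Compound-symmetry slope, ρ·SD1·SD2 / mean variance | 7.5/17 = 0.441 | 7.875/16.25 = 0.485 |
| Slope error | 0.392 | 0.158 |
| Bias | 0.392 × 0.09 × 3 = 0.106 | 0.158 × 0.09 × 3.5 = 0.050 |

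If the students lost are low scorers in the blended-learning arm, the shift is towards non-inferiority. With standard errors 5 × √(2/69) = 0.851 and 4.5 × √(2/69) = 0.766, the one-sided error becomes 1 − Φ(1.645 − 0.106/0.851) = 6.4% and 1 − Φ(1.645 − 0.050/0.766) = 5.7%.

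Simulation with 1,500 trials per setting and roughly 8 to 9% missing gave shifts of +0.11 and +0.05, with participant-robust errors of 7.2% and 6.3%. The Monte Carlo standard error there is √(0.05 × 0.95/1500) = 0.6 percentage points. An unstructured covariance with model-based errors gave no bias and 5.1%.

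**The case against.** The strongest objection is that the plan already specifies robust errors. A sandwich does not need the working covariance to be right, and the group-by-time term leaves the 6-month contrast free. This stands for participant-level clustering with dropout that does not differ by arm: Step 1 shows error near 5% whatever the two SDs. A reader might infer from the first table that equal variance by itself makes the planned limit wrong. The SAP does not support that, because those rates need model-based errors. Nor does it state a single residual variance; that is the usual reading of the random terms.

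Second, the three-site problem is one of too few clusters, not of unequal variance, and an unstructured covariance alone would not cure it. This is correct, and it is why the fix must also say how the standard error is obtained. A reader might also infer that the plan clusters on site. It does not say so: 6.2.1 lists dependence within sites, participants and series, and only the self-training analysis ties robust errors to site.

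Third, 6.2.3 offers a separate analysis of each time point. This removes the shared variance, but it reuses the same robust errors and site term and discards the first OSCE. Under Step 3 it sets the slope to zero, so its bias would be 0.833 × 0.09 × 3 = 0.22 or 0.643 × 0.09 × 3.5 = 0.20, in the same direction. It would not expose the misweighting.

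Fourth, non-inferiority also requires the per-protocol analysis to agree. That set excludes students who did not attend both exams, so under this dropout it is shifted the same way, and the proposed change does not alter that. The error rates above describe the full-set analysis alone.

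Last, the bias is small against a 1.5-point margin and largely cancels if dropout is similar in both arms. That also stands.

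**Conclusion.** The concern holds in a limited form. Clustered on participant, and with dropout unrelated to arm, the planned 6-month limit is close to nominal. The SAP does not secure those conditions.

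- **Cluster level.** If the sandwich is clustered on the three sites with a normal quantile, one-sided error is about 12% instead of 5%, whatever the SDs. This depends on how the unstated cluster level and reference distribution are resolved.
- **Missing second OSCE.** If the SDs differ and dropout depends on the first score and differs by arm, the 6-month difference is biased by roughly 0.05 to 0.11 points. The two SD pairs, the correlation of 0.5, about 9% missing and the dropout pattern are all assumptions. The statement in 6.3 about missing data therefore holds only if the covariance is right.

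The residual check in 6.2.5, the undefined trigger in 6.2.3 and the imputation rule in 6.3 would not reliably catch either problem. The first gap is the larger. The second is modest, but the same change to the model removes it.

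**What to change.** In SAP 6.2.1:

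- Replace the participant random intercept with an unstructured 2×2 residual covariance across the two time points within student (two variances and a free correlation).
- Keep the fixed effects, including group-by-time.
- Take the one-sided 6-month limit from this model's model-based standard error with small-sample degrees of freedom, for example Kenward-Roger or Satterthwaite, in place of the sandwich error, so that it does not rest on three site clusters.

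In 6.3, say that the handling of missing scores is conditional on this covariance.

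The cost is one extra variance parameter and the loss of nominal robustness to other misspecification. No new data are needed.

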3.2 Randomization

We will use centralized computed randomization in blocks of 4 to allocate each of the participants to one of the two study arms, with allocation in a 1:1 ratio, stratified by study site. The reason for block randomisation is the requirement of the control group to comprise of exactly 24 or 28 students due to the max. group size of 4 students per tutor. The randomization will be performed by an external partner (CTU Bern). An independent statistician of CTU Bern, who is not otherwise involved in the trial, will receive a list of participants of each site that contains the participant ID but no identifying data and will randomly allocate entries to either treatment arm. The generated allocation sequence will be password-protected and sent back to the trial coordinator. This procedure will ensure concealment of

allocation, i.e. randomization will be done without the influence from investigators or study personnel.

Figure 1: Study methods summary

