5.2 Eligibility

Students of human medicine at one of three Swiss universities (Bern, Freiburg, Zurich, in the 3rd to 8th semester) are eligible for study participation if they are:

- willing to participate in the study and give their consent to take part in the research;
- willing to pay the 200.- CHF course fees (partial reimbursement of tutors and administrative fee for the SGUM course certificate);
- fill out the baseline questionnaire.

Exclusion criteria for study participation are:

- Did not sign the study agreement or pay the course fee;
- More than 5 hours of previous formal ultrasound training;

• Failure to fill out baseline questionnaire.

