6.1.2 Secondary outcomes

- students' OSCE scores immediately after their courses (mean score); see description above
- additional hours of self-training during the follow-up phase;

Table 2:	Derivation	of primar	v and sec	condary	outcomes.
	20111011011	0. p	,		

Outcome	eCRF sheet	Variable	Variable type	Derivation	Outcome type
Primary: OSCE score six months after course	Excel sheet output from electronic data entry (iPad)	Subscores at OSCE stations 1-12	Numeric	Sum of scores at individual stations (0-50 pts) divided by number of stations	Continuous
OSCE score immediately after course	Excel sheet output from electronic data entry (iPad)	Subscores at OSCE stations 1-12	Numeric	Sum of scores at individual stations (0-50 pts) divided by number of stations	Continuous
Additional hours of self-training	Online Survey before 2 nd OSCE (RedCap)	Survey questions asking on additional self-training	Numeric	Simple number between e.g. 0-100 hours	Continuous

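### Self-training hours: the robust standard error meant to handle dependence within sites rests on only three clusters, so the interval and p-value of this secondary outcome are unreliable

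*SAP*

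**What the plan says.** Section 6.2.1 compares the arms on additional hours of self-training by the difference in medians: "The difference in median number of additional hours of self-training will be assessed from a quantile regression using robust standard errors". The same sentence gives the purpose of these errors, describing a "quantile regression using robust standard errors to account for dependence of data within sites". The result is to be reported with a two-sided 95% confidence interval and a p-value. Section 4.1 treats 0.05 two-sided as significant for secondary outcomes.

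The trial enrols "Students of human medicine at one of three Swiss universities" (Section 5.2). Students are randomised individually, "with allocation in a 1:1 ratio, stratified by study site" (Section 3.2). The outcome table in Section 6.1.2 records the hours as "Simple number between e.g. 0-100 hours".

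Section 6.2.3 adds sensitivity analyses for this outcome: "Depending on the distribution of the additional hours of self-training, we will furthermore use a non-parametric Wilcoxon-rank-sum test", or one of two negative binomial models, among them "a mixed-effects negative binomial model considering zero-inflation and a random term for sites".

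The SAP does not state a small-cluster correction, a reference distribution, an expected share of students with zero hours, or what to do if the median is zero in both arms.

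**The concern.** The phrase "robust standard errors to account for dependence of data within sites" describes a cluster-robust variance with site as the cluster. A standard error that is robust only to unequal variances does nothing about dependence. A cluster-robust variance is estimated from the variation between clusters, and it is reliable only when there are many of them. With three, it is too small on average and very unstable. The interval would be too narrow and the p-value too small, unless the reference distribution is changed in a way the SAP does not mention.

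The outcome shows whether the two arms practised equally between the course and the six-month examination. A spurious difference, or a missed one, would colour how the six-month scores are read.

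**Working it through.** **Inputs from the SAP.** Three sites (5.2); 1:1 allocation stratified by site (3.2); 69 per arm for analysis and 152 students included (3.3); two-sided 0.05 (4.1); hours from zero upward (6.1.2).

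**The plan's own figure.** The SAP gives none for this outcome. Its sample size for the primary outcome reproduces: 2 × (1.645 + 1.282)² × 4² / (1.5 + 0.5)² = 2 × 8.567 × 16 / 4 = 68.5, so 69 per arm and 138 in total; 138 / (1 − 0.09) = 151.6, so 152. These numbers serve below only as group sizes.

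**Step 1: approximation.** With G = 3 clusters, the estimate divided by its clustered standard error behaves roughly like t on G − 1 = 2 df, if the variance carries the factor G/(G − 1). For 2 df, P(|T| > c) = 1 − c/√(c² + 2).

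- With the factor, c = 1.96: 1 − 1.96/√5.842 = 1 − 1.96/2.417 = 0.189.
- Without it, the standard error shrinks by √(2/3), so c = 1.96 × 0.8165 = 1.600: 1 − 1.600/√4.56 = 1 − 1.600/2.135 = 0.251.
- The cut-off that restores 5% is 4.30, which is 4.30/1.96 = 2.2 times as large.

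**Step 2: simulation of the planned estimator.** Median regression with a site-clustered sandwich error (kernel density, Hall-Sheather bandwidth), no true group difference, 152 students, 1:1 within site. Assumptions that are not in the SAP: site sizes 52/48/52, 56/40/56 or 64/56/32; log-normal hours with log-SD 0.8; site SD 0 or 0.3 on the log scale.

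| Standard error and reference | Rejection at nominal 5% |
|---|---|
| 3 clusters, normal, no correction | 23-26% |
| 3 clusters, normal, with G/(G − 1) (52/48/52 only) | 17-19% |
| 3 clusters, t on 2 df | about 5-8% |
| 19 clusters, normal | 6.6% |
| Not clustered | about 4-5% |

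Without the correction, the three-cluster error averaged 0.72-0.74 of the true SD of the estimate, with a coefficient of variation of 54-60%.

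These figures are for hours with no mass at zero. With zeros mixed in (52/48/52), the clustered error with a normal reference rejected 21% at 20% zeros, 18% at 30%, 25% at 40% and 31% at 45%. The non-clustered error rejected about 2-3% at 20-30% zeros, but 11% at 40% and 14% at 45%.

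**Step 3: both medians zero.** With 69 per arm, an arm's median is zero when at least 35 students report zero. For the same true share p in both arms, the chance for both is P(Bin(69, p) ≥ 35)².

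| Share of zeros | One arm | Both arms |
|---|---|---|
| 40% | 0.046 | 0.2% |
| 45% | 0.202 | 4% |
| 50% | 0.500 | 25% |
| 55% | 0.798 | 64% |
| 60% | 0.954 | 91% |

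In the simulation, the kernel-based standard error could not be computed in 69% of runs at 55% zeros and in 95% at 60%.

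**The case against.** **The inflated error depends on an assumed reference distribution.** This is correct. The SAP names none, and t on 2 df nearly restores the level. But that choice is not in the plan, and it makes the multiplier 2.2 times as large.

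**The authors may mean robust errors without clustering.** These held about 4-5% for continuous hours, because stratified 1:1 allocation keeps the arms balanced within site. So it cannot be said that the test is invalid on every reading. That reading does not fit the purpose the sentence states, however, and the level was not held at 40-45% zeros.

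**A reader might infer that the SAP expects zero-inflation, so that the median comparison will end at zero against zero.** The document does not support this. Zero-inflation appears only as a conditional feature of sensitivity models, and no share of zeros is given. The chance of two zero medians runs from 0.2% to 91% over shares of 40% to 60%. If both true medians are zero, a difference of zero is the right answer to the question asked. Replacing the median by a mean or rank contrast throughout would be largely a preference about the estimand.

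**A rank test is already planned.** It is, and this softens the point about zeros. What remains is that the test is a sensitivity analysis, is not described as stratified by site, and has no rule for when it applies.

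**Conclusion.** The sentence is wrong as written. Read by its purpose, it clusters on three sites, and the resulting standard error, interval and p-value cannot be relied on. The two-sided error is about 17-26% with a normal reference and about 5-8% with t on 2 df. The approximation in Step 1 needs only the number of sites; the simulated figures also rest on the assumed site sizes and distribution of hours.

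The case of two zero medians is a conditional gap, not a predicted failure. It matters if about half or more of each arm reports no extra training, which the SAP neither states nor rules out.

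A reader might also infer that the trial's main conclusion is at risk. It is not: this is one of two secondary outcomes, and the claim of non-inferiority does not depend on it.

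**What to change.** In Section 6.2.1, remove the site-clustered robust standard error for this outcome. Enter site as fixed indicators in the quantile regression. Obtain the 95% interval and p-value from a bootstrap that resamples students within site and arm, or obtain the p-value by permuting allocation within site. The group coefficient then reads as a difference in medians at a given site, taken as common to the three sites, and the text should say so.

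Add one rule for zeros: if the median is zero in both arms, the p-value comes from the Wilcoxon test of Section 6.2.3, stratified by site (van Elteren), reported with the proportion of students in each arm who did any extra training.

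The cost is a change of wording and slightly more analysis work. No new data are needed. If Section 6.3 brings in multiple imputation for this outcome, the SAP should also say how the bootstrap or rank result is combined across the imputed data sets.
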